##### 3.2.1 Additional instructions, requirements and exceptions for protocol EAY131 – Subprotocol Z1D

#### **Additional Instructions**

For instructions on how to specifically report events that result in persistent or significant disability/incapacity, congenital anomaly, or birth defect events via CTEP-AERS, please contact the AEMD Help Desk at [[contact]](mailto:[contact]) or [contact]. This will need to be discussed on a case-by-case basis.

#### **EAY131 – Subprotocol Z1D specific expedited reporting requirements:**

- **Pregnancies:** Pregnancies and suspected pregnancies (including a positive or inconclusive pregnancy test, regardless of age or disease state) occurring while the subject is on nivolumab, or within 28 days of the subject's last dose of nivolumab, are considered immediately reportable events. The pregnancy, suspected pregnancy, or positive/ inconclusive pregnancy test must be reported via CTEP-AERS within 24 hours of the Investigator's knowledge. Please refer to Appendix VIII in MATCH Master Protocol for detailed instructions on how to report the occurrence of a pregnancy as well as the outcome of all pregnancies.

**EAY131 – Subprotocol Z1D specific expedited reporting exceptions:**

For Subprotocol Z1D, the adverse events listed below **do not** require expedited reporting via CTEP-AERS:

- If an AE meets the reporting requirements of the protocol, and it is listed on the SPEER, it should **ONLY** be reported via CTEP-AERS if the grade being reported exceeds the grade listed in the parentheses next to the event.

3.2.2 Second Primary Cancer Reporting Requirements

All cases of second primary cancers, including acute myeloid leukemia (AML) and myelodysplastic syndrome (MDS), that occur following treatment on NCI-sponsored trials must be reported to ECOG-ACRIN using Medidata Rave

- **A second malignancy is a cancer that is UNRELATED to any prior anti-cancer treatment (including the treatment on this protocol). Second malignancies require ONLY routine reporting as follows:**
  1. Complete a Second Primary Form in Medidata Rave within 14 days.
  2. Upload a copy of the pathology report to ECOG-ACRIN via Medidata Rave confirming the diagnosis.
  3. If the patient has been diagnosed with AML/MDS, upload a copy of the cytogenetics report (if available) to ECOG-ACRIN via Medidata Rave.
- **A secondary malignancy is a cancer CAUSED BY any prior anti-cancer treatment (including the treatment on this protocol). Secondary malignancies require both routine and expedited reporting as follows:**
  1. Complete a Second Primary Form in Medidata Rave within 14 days
  2. Report the diagnosis via CTEP-AERS at <http://ctep.cancer.gov>  
*Report under a.) leukemia secondary to oncology chemotherapy, b.) myelodysplastic syndrome, or c.) treatment related secondary malignancy*
  3. Upload a copy of the pathology report to ECOG-ACRIN via Medidata Rave and submit a copy to NCI/CTEP confirming the diagnosis.
  4. If the patient has been diagnosed with AML/MDS, upload a copy of the cytogenetics report (if available) to ECOG-ACRIN via Medidata Rave and submit a copy to NCI/CTEP.

**NOTE:** The Second Primary Form and the CTEP-AERS report should not be used to report recurrence or development of metastatic disease.

**NOTE:** If a patient has been enrolled in more than one NCI-sponsored study, the Second Primary Form must be

submitted for the most recent trial. ECOG-ACRIN must be provided with a copy of the form and the associated pathology report and cytogenetics report (if available) even if ECOG-ACRIN was not the patient's most recent trial.

**NOTE:** Once data regarding survival and remission status are no longer required by the protocol, no follow-up data should be submitted via CTEP-AERS or by the Second Primary Form.

Rev. 3/17  
Rev. Add15

3.3 Comprehensive Adverse Events and Potential Risks List (CAEPR) for BMS-936558 (Nivolumab, MDX-1106, NSC 748726)

The Comprehensive Adverse Events and Potential Risks list (CAEPR) provides a single list of reported and/or potential adverse events (AE) associated with an agent using a uniform presentation of events by body system. In addition to the comprehensive list, a subset, the Specific Protocol Exceptions to Expedited Reporting (SPEER), appears in a separate column and is identified with bold and italicized text. This subset of AEs (SPEER) is a list of events that are protocol specific exceptions to expedited reporting to NCI (except as noted below). Refer to the 'CTEP, NCI Guidelines: Adverse Event Reporting Requirements' [http://ctep.cancer.gov/protocolDevelopment/electronic\\_applications/docs/aeGUIDELINES.pdf](http://ctep.cancer.gov/protocolDevelopment/electronic_applications/docs/aeGUIDELINES.pdf) for further clarification. *Frequency is provided based on 2069 patients.* Below is the CAEPR for BMS-936558 (Nivolumab, MDX-1106).

**NOTE:** If an AE meets the reporting requirements of the protocol, and it is listed on the SPEER, it should **ONLY** be reported via CTEP-AERS if **the grade being reported exceeds the grade listed in the parentheses next to the event in the SPEER.**

Version 2.3, June 18, 2018

Adverse Events with Possible Relationship to BMS-936558 (Nivolumab, MDX-1106) (CTCAE 5.0 Term) [n= 2069]			Specific Protocol Exceptions to Expedited Reporting (SPEER)
Likely (>20%)	Less Likely (<=20%)	Rare but Serious (<3%)	
BLOOD AND LYMPHATIC SYSTEM DISORDERS			
	Anemia		Anemia (Gr 2)
CARDIAC DISORDERS			
		Cardiac disorders - Other (cardiomyopathy)	
		Myocarditis	
		Pericardial tamponade 	
		Pericarditis	
ENDOCRINE DISORDERS			
	Adrenal insufficiency 		
	Hypophysitis 		
	Hyperthyroidism 		
	Hypothyroidism 		
EYE DISORDERS			
		Blurred vision	
		Dry eye	
		Eye disorders - Other (diplopia) 	
		Eye disorders - Other (Graves ophthalmopathy) 	
		Eye disorders - Other (optic neuritis retrobulbar) 	
	Uveitis		
GASTROINTESTINAL DISORDERS			
	Abdominal pain		Abdominal pain (Gr 2)
	Colitis 		

Adverse Events with Possible Relationship to BMS-936558 (Nivolumab, MDX-1106) (CTCAE 5.0 Term) [n= 2069]			Specific Protocol Exceptions to Expedited Reporting (SPEER)
Likely (>20%)	Less Likely (<=20%)	Rare but Serious (<3%)	
		Colonic perforation 	
	Diarrhea		Diarrhea (Gr 3)
	Dry mouth		Dry mouth (Gr 2)
		Gastritis	
		Mucositis oral	
	Nausea		Nausea (Gr 2)
	Pancreatitis 		
GENERAL DISORDERS AND ADMINISTRATION SITE CONDITIONS			
Fatigue			Fatigue (Gr 3)
	Fever		Fever (Gr 2)
	Injection site reaction		Injection site reaction (Gr 2)
IMMUNE SYSTEM DISORDERS			
		Allergic reaction 	
		Autoimmune disorder 	
		Cytokine release syndrome 	
		Immune system disorders - Other (GVHD in the setting of allotransplant) 	
		Immune system disorders - Other (sarcoid granuloma) 	
INJURY, POISONING AND PROCEDURAL COMPLICATIONS			
	Infusion related reaction 		
INVESTIGATIONS			
	Alanine aminotransferase increased 		Alanine aminotransferase increased (Gr 3)
	Aspartate aminotransferase increased 		Aspartate aminotransferase increased (Gr 3)
	Blood bilirubin increased 		Blood bilirubin increased (Gr 2)
	Creatinine increased		
	Lipase increased		
	Lymphocyte count decreased		Lymphocyte count decreased (Gr 2)
	Neutrophil count decreased		
	Platelet count decreased		
	Serum amylase increased		
METABOLISM AND NUTRITION DISORDERS			
	Anorexia		
		Hyperglycemia	Hyperglycemia (Gr 2)
		Metabolism and nutrition disorders - Other (diabetes mellitus with ketoacidosis) 	
MUSCULOSKELETAL AND CONNECTIVE TISSUE DISORDERS			
	Arthralgia		
		Musculoskeletal and connective tissue disorder - Other (polymyositis)	

Adverse Events with Possible Relationship to BMS-936558 (Nivolumab, MDX-1106) (CTCAE 5.0 Term) [n= 2069]			Specific Protocol Exceptions to Expedited Reporting (SPEER)
Likely (>20%)	Less Likely (<=20%)	Rare but Serious (<3%)	
		Myositis	
		Rhabdomyolysis	
NERVOUS SYSTEM DISORDERS			
		Encephalopathy 	
		Facial nerve disorder 	
		Guillain-Barre syndrome 	
		Myasthenia gravis 	
		Nervous system disorders - Other (demyelination myasthenic syndrome)	
		Nervous system disorders - Other (encephalitis) 	
		Nervous system disorders - Other (meningoencephalitis)	
		Nervous system disorders - Other (meningoradiculitis) 	
		Nervous system disorders - Other (myasthenic syndrome)	
		Peripheral motor neuropathy	
		Peripheral sensory neuropathy	
		Reversible posterior leukoencephalopathy syndrome 	
RENAL AND URINARY DISORDERS			
		Acute kidney injury 	
RESPIRATORY, THORACIC AND MEDIASTINAL DISORDERS			
	Pleural effusion 		
	Pneumonitis 		
		Respiratory, thoracic and mediastinal disorders - Other (bronchiolitis obliterans with organizing pneumonia) 	
SKIN AND SUBCUTANEOUS TISSUE DISORDERS			
		Erythema multiforme 	
	Pruritus 		Pruritus (Gr 2)
	Rash maculo-papular 		Rash maculo-papular (Gr 2)
		Skin and subcutaneous disorders -Other (bullous pemphigoid)	
	Skin and subcutaneous disorders - Other (Sweet's Syndrome) 		
	Skin hypopigmentation 		
		Stevens-Johnson syndrome	
		Toxic epidermal necrolysis	

This table will be updated as the toxicity profile of the agent is revised. Updates will be distributed to all Principal Investigators at the time of revision. The current version can be obtained by contacting [[contact]](mailto:[contact]). Your name, the name of the investigator, the protocol and the agent should be included in the e-mail.

Pericardial tamponade may be related to possible inflammatory reaction at tumor site.

BMS-936558 (Nivolumab, MDX-1106) being a member of class of agents involved in the inhibition of “immune checkpoints”, may result in severe and possibly fatal immune-mediated adverse events probably due to T-cell activation and proliferation. This may result in autoimmune disorders that can include (but are not limited to) autoimmune hemolytic anemia, acquired anti-factor VIII immune response, autoimmune aseptic meningitis, autoimmune hepatitis, autoimmune nephritis, autoimmune neuropathy, autoimmune thyroiditis, bullous pemphigoid, exacerbation of Churg-Strauss Syndrome, drug rash with eosinophilia systemic symptoms [DRESS] syndrome, facial nerve disorder (facial nerve paralysis), limbic encephalitis, hepatic failure, pure red cell aplasia, pancreatitis, ulcerative and hemorrhagic colitis, endocrine disorders (e.g., autoimmune thyroiditis, hyperthyroidism, hypothyroidism, autoimmune hypophysitis/hypopituitarism, thyrotoxicosis, and adrenal insufficiency), sarcoid granuloma, myasthenia gravis, polymyositis, and Guillain-Barre syndrome.

 Pancreatitis may result in increased serum amylase and/or more frequently lipase.

Cytokine release syndrome may manifest as hemophagocytic lymphohistiocytosis with accompanying fever and pancytopenia.

Complications including hyperacute graft-versus-host disease (GVHD), some fatal, have occurred in patients receiving allo stem cell transplant (SCT) after receiving BMS-936558 (Nivolumab, MDX-1106). These complications may occur despite intervening therapy between receiving BMS-936558 (Nivolumab, MDX-1106) and allo-SCT.

Infusion reactions, including high-grade hypersensitivity reactions which have been observed following administration of nivolumab, may manifest as fever, chills, shakes, itching, rash, hypertension or hypotension, or difficulty breathing during and immediately after administration of nivolumab.

**Adverse events reported on BMS-936558 (Nivolumab, MDX-1106) trials, but for which there is insufficient evidence to suggest that there was a reasonable possibility that BMS-936558 (Nivolumab, MDX-1106) caused the adverse event:**

**BLOOD AND LYMPHATIC SYSTEM DISORDERS** - Leukocytosis

**CARDIAC DISORDERS** - Atrial fibrillation; Atrioventricular block complete; Heart failure; Ventricular arrhythmia

**EAR AND LABYRINTH DISORDERS** - Vestibular disorder

**EYE DISORDERS** - Eye disorders - Other (iritocyclitis); Optic nerve disorder; Periorbital edema

**GASTROINTESTINAL DISORDERS** - Constipation; Duodenal ulcer; Flatulence; Gastrointestinal disorders - Other (mouth sores); Vomiting

**GENERAL DISORDERS AND ADMINISTRATION SITE CONDITIONS** - Chills; Edema limbs; Malaise; Pain

**HEPATOBIILIARY DISORDERS** - Bile duct stenosis

**IMMUNE SYSTEM DISORDERS** - Anaphylaxis; Immune system disorders - Other (autoimmune thrombotic microangiopathy); Immune system disorders - Other (limbic encephalitis)

**INFECTIONS AND INFESTATIONS** - Bronchial infection; Lung infection; Sepsis; Upper respiratory infection

**INVESTIGATIONS** - Blood lactate dehydrogenase increased; GGT increased; Investigations - Other (protein total decreased); Lymphocyte count increased; Weight loss

**METABOLISM AND NUTRITION DISORDERS** - Dehydration; Hyperuricemia; Hypoalbuminemia; Hypocalcemia; Hyponatremia; Hypophosphatemia

**MUSCULOSKELETAL AND CONNECTIVE TISSUE DISORDERS** - Back pain;

Musculoskeletal and connective tissue disorder - Other (musculoskeletal pain); Musculoskeletal and connective tissue disorder - Other (polymyalgia rheumatica); Myalgia; Pain in extremity

**NEOPLASMS BENIGN, MALIGNANT AND UNSPECIFIED (INCL CYSTS AND POLYPS) -**

Neoplasms benign, malignant and unspecified (incl cysts and polyps) - Other (histiocytic necrotizing lymphadenitis)

**NERVOUS SYSTEM DISORDERS** - Dizziness; Headache; Intracranial hemorrhage

**PSYCHIATRIC DISORDERS** - Insomnia

**RENAL AND URINARY DISORDERS** - Hematuria; Renal and urinary disorders - Other (tubulointerstitial nephritis)

**RESPIRATORY, THORACIC AND MEDIASTINAL DISORDERS** - Bronchospasm; Cough; Dyspnea; Hypoxia

**SKIN AND SUBCUTANEOUS TISSUE DISORDERS** - Alopecia; Dry skin; Hyperhidrosis; Pain of skin; Photosensitivity; Rash acneiform; Skin and subcutaneous tissue disorders - Other (rosacea)

**VASCULAR DISORDERS** - Flushing; Hypertension; Hypotension; Vasculitis

**NOTE:** BMS-936558 (Nivolumab, MDX-1106) in combination with other agents could cause an exacerbation of any adverse event currently known to be caused by the other agent, or the combination may result in events never previously associated with either agent

3.4 Dose Modifications

All toxicity grades below are described using the NCI Common Terminology Criteria for Adverse Events (CTCAE) version 4.0.

All appropriate treatment areas should have access to a copy of the CTCAE version 4.0. A copy of the CTCAE version 4.0 can be downloaded from the CTEP website (<http://ctep.cancer.gov>).

*Please refer to the Nivolumab Investigator Brochure or [Appendix II](#) to the protocol for toxicity management algorithms which include specific treatment guidelines. These algorithms should be followed unless there are specific clinical circumstances for which the treating physician decides an alternative treatment approach is clinically appropriate. Consultation with the study chair is recommended.*

*In all of the tables for dose modification and holds in this section, the guidelines are for adverse events thought at least possibly attributed to study drug. Generally we strongly encourage early evaluation while withholding drug, and appropriate treatment as indicated in the management tables and event specific guidelines.*

Rev. 3/17

ALL OTHER EVENTS	Management/Next Dose for Nivolumab
≤ Grade 1	No change in dose
Grade 2	Hold until ≤ Grade 1 OR baseline (exceptions as noted below)
Grade 3	Off protocol therapy (exceptions as noted below)
Grade 4	Off protocol therapy
Recommended management: As clinically indicated	

- Any grade 2 drug-related uveitis or eye pain or blurred vision that does not respond to topical therapy and does not improve to Grade 1 severity within the re-treatment period OR requires systemic treatment should go off protocol treatment
- Any adverse event, laboratory abnormality, or intercurrent illness which, in the judgment of the investigator, presents a substantial clinical risk to the subject with continued study drug dosing should go off protocol treatment.
- Any grade 2-4 drug-related laboratory abnormality or electrolyte abnormality, that can be managed independently from underlying organ pathology with electrolyte replacement, hormone replacement, transfusion or insulin or that does not require treatment does not require hold/discontinuation.
- Tolerable and clinically stable grade 2 toxicities attributed to study drug may remain on study with PI approval (e.g. thrombosis that is being anticoagulated)

Rev. 12/16

Rev. 3/17

Rev. 3/17

Skin Rash and Oral Lesions	Management/Next Dose for Nivolumab
≤ Grade 1	No change in dose *
Grade 2	Treatment may continue at investigator discretion. A short course of steroids is permitted. If treatment is held, resume at same dose level.
Grade 3	Hold* until ≤ Grade 1. Resume at same level at investigator discretion
Grade 4	Off protocol therapy
* Patients with purpuric or bullous lesions must be evaluated for vasculitis, Steven-Johnson syndrome, TEN, and autoimmune bullous disease including oral lesions of bullous pemphigus/pemphagoid. Pruritus may occur with or without skin rash and should be treated symptomatically if there is no associated liver or GI toxicity. Note skin rash typically occurs early and may be followed by additional events particularly during steroids tapering.	
Recommended management: AE management guidelines	

Rev. 3/17

Liver Function AST, ALT, Bilirubin	Management/Next Dose for Nivolumab
≤ Grade 1	Treatment may be continued at investigator discretion. Dose level is maintained.
Grade 2	Hold until UNL or baseline. Resume at same dose level.
Grade 3	Off protocol therapy
Grade 4	Off protocol therapy
* I-O therapy may be delayed rather than discontinued if AST/ALT ≤ 8 x ULN and T.bili ≤ 5 x ULN Continued treatment of active immune mediated hepatitis may exacerbate ongoing inflammation. Holding drug to evaluate LFT changes and early treatment are recommended. ** LFT changes may occur during steroid tapers from other events and may occur together with other GI events including cholecystitis/pancreatitis.	
Recommended management: see Hepatic AE management algorithm	

Rev. 3/17

Diarrhea/ Colitis	Management/Next Dose for Nivolumab
≤ Grade 1	Symptomatic treatment but continue therapy. No change in dose
Grade 2	Hold until baseline. No change in dose
Grade 3	Hold until baseline. No change in dose.
Grade 4	Off protocol therapy
See GI AE Algorithm for management of symptomatic colitis. Patients with grade 2 symptoms but normal colonoscopy and biopsies may be retreated after resolution. Please evaluate pituitary function prior to starting steroids if possible without compromising acute care. Evaluation for all patients for additional causes includes C. diff , acute and self-limited infectious and foodborne illness, ischemic bowel, diverticulitis, and IBD.	
Recommended management: see GI AE management Algorithm	

Symptomatic Pancreatitis	Management/Next Dose for Nivolumab
≤ Grade 1	Continue therapy.
Grade 2	Continue therapy.
Grade 3	Patients who develop symptomatic pancreatitis or DM should be taken off treatment
Grade 4	Patients who develop symptomatic pancreatitis or DM should be taken off treatment

Patients with any grade lipase/amylase elevation may continue treatment at investigator discretion if asymptomatic.
 
Patients may develop symptomatic and radiologic evidence of pancreatitis as well as DM and DKA. Lipase elevation may occur during the period of steroid withdrawal and with other immune mediated events or associated with colitis, hepatitis, and patients who have asymptomatic lipase elevation typically have self-limited course and may be retreated.
 
For treatment management of symptomatic pancreatitis please follow the Hepatic Adverse Event Management Algorithm
	

Pneumonitis	Management/Next Dose for Nivolumab
≤ Grade 1	Hold dose pending evaluation and resolution to baseline including baseline pO2. Resume no change in dose after pulmonary and/or ID consultation excludes lymphocytic pneumonitis.
Grade 2	Hold dose pending evaluation. Resume no change in dose after pulmonary and/or ID consultation excludes nivolumab and associated lymphocytic pneumonitis as the cause of the pneumonitis. Off study if steroids are required. ^
Grade 3	Hold dose pending evaluation. Refer to Appendix II for diagnostic and treatment guidelines.
Grade 4	Off protocol therapy

Distinguishing inflammatory pneumonitis is often a diagnosis of exclusion for patients who do not respond to antibiotics and have no causal organism identified including influenza. Most patients with respiratory failure or hypoxia will be treated with steroids. Bronchoscopy may be required and analysis of lavage fluid for lymphocytic predominance may be helpful. Patients with new lung nodules should be evaluated for sarcoid like granuloma. Please consider recommending seasonal influenza killed vaccine for all patients.
	
Recommended management: See Pulmonary Adverse Event Management Algorithm	

Fatigue	Management/Next Dose for Nivolumab
≤ Grade 1	No change in dose.
Grade 2	No change in dose
Grade 3	Hold until ≤ Grade 2. Resume at same dose level

Fatigue is the most common adverse event associated with immune checkpoint therapy. Grade 2 or greater fatigue should be evaluated for associated or underlying organ involvement including pituitary, thyroid, and hepatic, or muscle (CPK) inflammation
	

Neurologic events	Management/Next Dose for Nivolumab
≤ Grade 1	Hold dose pending evaluation and observation. Resume with no change in dose when resolved to baseline.
Grade 2	Hold dose pending evaluation and observation. # Hold until ≤ Grade 1. Off protocol therapy if treatment with steroids is required. Resume at same dose level for peripheral isolated n. VII (Bell's palsy)
Grade 3	Off protocol therapy
Grade 4	Off protocol therapy
Patients with any CNS events including aseptic meningitis, encephalitis, symptomatic hypophysitis, or myopathy, peripheral demyelinating neuropathy, cranial neuropathy (other than peripheral n. VII), GB syndrome, myasthenia gravis should be off study.	
Recommended management: See Neurologic Adverse Event Management Algorithm	

Endocrine Hypophysitis Adrenal Insufficiency	Management/Next Dose for Nivolumab
≤ Grade 1	Asymptomatic TSH elevation * May continue therapy pending evaluation, consider endocrine consult
Grade 2	Hold until patients are on a stable replacement hormone regimen. If treated with steroids patients must be stable off steroids for two weeks. Resume at same dose level.
Grade 3	See Appendix II for diagnostic and management algorithm.
Grade 4	See Appendix II for diagnostic and management algorithm.
Note all patients with symptomatic pituitary enlargement, exclusive of hormone deficiency, but including severe headache or enlarged pituitary on MRI should be considered grade 3 events. Isolated thyroid or testosterone deficiency may be treated as grade 2 if there are no other associated deficiencies and adrenal function is monitored. Please evaluate pituitary function before beginning steroid therapy or replacement therapy of any kind. *Note patients with thyroiditis may be retreated on replacement therapy. Patients must be evaluated to rule out pituitary disease prior to initiating thyroid replacement.	
Recommended management: See Endocrine Management Algorithm	

Rev. 3/17

Renal	Management/Next Dose for Nivolumab combination
≤ Grade 1	May continue therapy per investigator discretion.
Grade 2	Hold until ≤ Grade 1. Resume at same dose level.
Grade 3	Hold until ≤ Grade 1. Resume at same dose level.
Grade 4	Off treatment

Infusion reaction	Management/Next Dose for Nivolumab combination
≤ Grade 1	May continue therapy per investigator discretion.
Grade 2	Hold until ≤ Grade 1. Resume at same dose level.
Grade 3	Hold until ≤ Grade 1. Resume at same dose level.
Grade 4	Off treatment
Patients with fever should be evaluated as clinically appropriate. Patients may experience isolated fever during infusion reactions or up to several days after infusion. Evaluation over the course of 1-2 weeks should be done for other autoimmune events that may present as fever	

Fever	Management/Next Dose for Nivolumab combination
≤ Grade 1	Evaluate and continue at same dose level
Grade 2	Hold until ≤ Grade 1. Resume at same dose level.
Grade 3	Hold until ≤ Grade 1. Resume at same dose level.
Grade 4	Off treatment
Patients with fever should be evaluated as clinically appropriate. Patients may experience isolated fever during infusion reactions or up to several days after infusion. Evaluation over the course of 1-2 weeks should be done for other autoimmune events that may present as fever	
See Section 5 . Infusion reactions	

Rev. 3/17

Cardiac*	Management/Next Dose for BMS-936558 (Nivolumab) Cardiac Toxicities
≤ Grade 1	Hold dose pending evaluation and observation.** Evaluate for signs and symptoms of CHF, ischemia, arrhythmia or myositis. Obtain history EKG, CK (for concomitant myositis), CK-MB. Repeat troponin, CK and EKG 2-3 days. If troponin and labs normalize may resume therapy. If labs worsen or symptoms develop then treat as below. Hold pending evaluation
Grade ≥ 2 with suspected myocarditis	Hold dose.** Admit to hospital. Cardiology consult. Rule out MI and other causes of cardiac disease. Cardiac Monitoring. Cardiac Echo. Consider cardiac MRI and cardiac biopsy. Initiate high dose methylprednisolone. If no improvement within 24 hours, add either infliximab, ATG or tacrolimus. Resume therapy if there is a return to baseline and myocarditis is excluded or considered unlikely.
Grade ≥ 2 with confirmed myocarditis	Off protocol therapy. Admit to CCU (consider transfer to nearest Cardiac Transplant Unit). Treat as above. Consider high dose methylprednisolone. Add ATG or tacrolimus if no improvement. Off treatment.

* Including CHF, LV systolic dysfunction, Myocarditis, CPK, and troponin
 
** Patients with evidence of myositis without myocarditis may be treated according as "other event"
 
Note: The optimal treatment regimen for immune mediated myocarditis has not been established. Since this toxicity has caused patient deaths, an aggressive approach is recommended.
	

- Drug will be held for grade 2 cardiac dysfunction pending evaluation
- Drug will be permanently discontinued for grade 3 or 4 cardiac dysfunction and grade 2 events that do not recover to baseline or that reoccur
- Treatment with steroids as clinically indicated

If treatment is delayed >6 weeks for an adverse event, the study PI must be consulted for any consideration of further therapy.

Patients with grade 3 thyroiditis and skin rash may continue therapy as for grade 2 events with resolution and stable replacement treatment.

Patients with thyroiditis or hypopituitarism who are stable as above may be restarted with replacement hormones including thyroid hormone and physiologic doses of corticosteroids.

Please note that grading and for hypophysitis with symptoms of headache, visual or neurologic changes or radiologic evidence of pituitary enlargement and other CNS events such as aseptic meningitis or encephalitis should be considered grade 3 events.

Any patients who require additional immune suppressive treatment beyond steroids should go off study treatment

Patients requiring > two dose delays for the same event should go off protocol therapy.

Prior to starting corticosteroids or hormone replacement for any reason, appropriate endocrine testing including cortisol, ACTH, TSH and T4 should be obtained to document baseline. However, if urgent steroid use is clinically required, steroid treatment should not be delayed for bloodwork.

Please note that in some cases the treatment algorithms recommend steroids if symptoms do not resolve in 7 days. However, this recommendation is not meant to delay steroid treatment at any time it is clinically indicated.

Patients may be dose-delayed for evaluation and restarted depending on results.

Any patient started on corticosteroids initially who is determined to not require steroid treatment for an autoimmune adverse event may resume therapy after a 2 week observation period without further symptoms at the discretion of the PI or investigator.

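### The skin table requires purpuric or bullous lesions to be evaluated for SJS/TEN, but it orders no hold during the evaluation below Grade 3 and lets a Grade 3 rash resume without SJS/TEN being excluded

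*Protocol*

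**What the plan says.** The skin rash and oral lesions table in Protocol Section 3.4 has four rows and a footnote marked by an asterisk.

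- **Grade 1 or below:** "No change in dose", with the asterisk.
- **Grade 2:** "Treatment may continue at investigator discretion. A short course of steroids is permitted". If the drug is held, it restarts at the same dose. This row has no asterisk.
- **Grade 3:** "Hold* until ≤ Grade 1. Resume at same level at investigator discretion". The asterisk sits on the word for holding.
- **Grade 4:** protocol therapy ends.

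The footnote is mandatory and its wording is not limited by grade: "Patients with purpuric or bullous lesions must be evaluated for vasculitis, Steven-Johnson syndrome, TEN, and autoimmune bullous disease". It adds: "Note skin rash typically occurs early and may be followed by additional events particularly during steroids tapering". For management, the table points to adverse event guidelines in general terms.

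Elsewhere, the risk list in Section 3.3 includes SJS and "Toxic epidermal necrolysis" among the rare but serious events, and Section 2.1.7 bars patients with a history of either from entering.

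**The concern.** An evaluation is ordered for two grave diagnoses, but the rows say neither what happens to dosing while it is under way nor what follows from its result. An investigator who follows the rows literally may infuse a patient with a low-grade bullous or purpuric eruption before the result is known. The same investigator may restart a Grade 3 patient at the same dose once the rash has improved, whatever the evaluation showed.

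Timing makes the first case plausible. The footnote says rash tends to come early, and under Section 3.1 doses are two weeks apart for the first 4 cycles. A result could therefore arrive after the next infusion, although the protocol gives no turnaround time for the evaluation.

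What is at stake is patient safety and uniform handling across sites. Sample size and analysis are not affected.

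**Working it through.** No power or error-rate calculation applies. The check is a row-by-row reading of the skin table, a comparison with sibling tables in Section 3.4, and a test of whether general text closes the gap.

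**Step 1. The skin table.**

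| Grade | Hold required during evaluation? | Further dosing allowed? | Exclusion of SJS/TEN required first? |
|---|---|---|---|
| 1 or below | No | Yes | No |
| 2 | No (optional) | Yes | No |
| 3 | Yes | Yes, once at Grade 1 or below | No |
| 4 | Therapy ends | No | Does not arise |

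Rows allowing a dose during the evaluation: 2 of 4. Rows allowing further dosing that require SJS/TEN to be excluded: 0 of 3. The table names no outcome for a confirmed case below Grade 4.

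**Step 2. Sibling tables in Section 3.4.**

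- *Pneumonitis, Grade 1 or below and Grade 2:* hold, then resume only after a pulmonary or infectious-disease consultation has excluded the drug-related diagnosis.
- *Cardiac, Grade 2 or above with suspected myocarditis:* hold, then resume on return to baseline if myocarditis has been ruled out or judged unlikely. Confirmed myocarditis ends protocol therapy.
- *Endocrine and fever, Grade 1 or below:* dosing may go on during evaluation. Dosing during a work-up is therefore not unusual in itself; what sets the skin table apart is the gravity of the diagnoses it names.

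**Step 3. General text.**

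- The opening of Section 3.4 strongly encourages withholding drug during evaluation. That is advice.
- A later sentence in Section 3.4 permits a delay for evaluation, with restart according to the results. That is permissive.
- The substantial-risk rule in Section 3.4 and the unacceptable-toxicity criterion in Section 3.6 end treatment on judgment, without naming SJS or TEN.

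None of these orders a hold or makes resumption conditional on the diagnosis. The same general text covers pneumonitis and myocarditis, where explicit rules were written all the same.

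**Step 4. Which table governs a confirmed case.** Under the table for all other events, Grade 3 means leaving protocol therapy, subject to listed exceptions. Under the skin table, Grade 3 means hold and possibly resume. Section 3.4 does not say which applies to confirmed SJS or TEN.

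**Step 5. How often.** Inputs: the below-3% category in Section 3.3, and the accrual goal of 70 in the Schema. Ceiling per term: 0.03 × 70 = 2.1 patients. This is an upper limit from a category boundary, not an estimate. It counts all cases, not only those dosed during an evaluation. The protocol gives no rate for bullous or purpuric rash.

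**The case against.** The strongest objection is that half of the instruction cannot be seen. Section 3.4 says the Appendix II algorithms should be followed, and Section 3.5.1 describes the Appendix II care as required. The skin flowchart in Appendix II is lost from the text available here, and what is lost in this way cannot be counted as absent. This stands, and it confines the point to the table. It does not remove the point: if the flowchart does require a hold and exclusion, the rows still allow dosing and would need to be aligned with it.

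Second, grading follows CTCAE 4.0, and nothing here shows that SJS or TEN can carry a grade at which dosing continues. This also stands against any claim that a *confirmed* case would be dosed at Grade 1 or 2. It does not reach the lesion still under evaluation, whose diagnosis is open, nor the Grade 3 row.

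Third, a confirmed case reads naturally under all other events, since the risk list treats SJS and TEN as terms separate from rash. That is reasonable, but the reader has to infer it, and the two tables give opposite actions at Grade 3.

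Fourth, the footnote also names vasculitis and autoimmune bullous disease, so gating resumption on SJS/TEN alone is selective. That is fair. The proposed hold lasts until the whole evaluation is complete, and the sponsor could widen the resumption condition.

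**Conclusion.** The point holds for the skin table in Section 3.4. Evaluation for SJS/TEN is mandatory, but no hold is required during it at Grade 1 or below or at Grade 2. The Grade 3 row allows same-dose resumption on severity and discretion, without the diagnosis being excluded. This departs from the protocol's own pattern for pneumonitis and suspected myocarditis, and fits poorly with the entry exclusion in Section 2.1.7. It deserves correction, with medium confidence because the flowchart is unseen.

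Three stronger readings are tempting but unsupported.

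- A reader might infer that the protocol as a whole has no safeguard against redosing in SJS/TEN. The general text offers discretionary safeguards, and the flowchart may contain a binding one.
- A reader might combine the two-week interval with the 17 to 25 day half-life in Section 1.1.3 and treat the drug remaining from one infusion as a measure of harm. That describes exposure to one dose, ignores drug already on board, and says nothing about added risk.
- A reader might see a contradiction between the skin table and the later sentence in Section 3.4 that lets Grade 3 skin rash be handled as Grade 2. That sentence is loosely worded but not contradictory, and it can stay as it is.

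**What to change.** Add to the skin table footnote: *For purpuric or bullous lesions, hold nivolumab at any grade until this evaluation is complete; resume only if SJS and TEN are excluded; confirmed SJS or TEN: off protocol therapy.* Add the asterisk to the Grade 2 row so that the footnote plainly attaches to it.

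Check the Appendix II skin flowchart first. If it already says this, cite it in the footnote and align the rows for Grade 1 or below through Grade 3 with it.

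The cost is one footnote addition and one asterisk in the next amendment. The clinical downside is an occasional delayed dose for lesions that prove benign. Such a delay counts toward the Section 3.4 rule that ends protocol therapy after more than two delays for the same event; the sponsor may want to say whether a negative evaluation should count. Sample size and data collection are unaffected.
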